2.3.8 Analysis sets

The number (%) of subjects in each analysis set (defined in [Section 2.2](#)) will be summarized by treatment arm and stratum.

2.4 Treatments (study treatment, rescue medication, concomitant therapies, compliance)

2.4.1 Study treatment / compliance

Duration of exposure, average cycle dose and actual cumulative dose, dose intensity (DI) and relative dose intensity (RDI) will be summarized by treatment arm, separately for each component of study treatment. The duration of exposure will also be presented for the study treatment (LAG525 + spartalizumab, LAG525 + spartalizumab + carboplatin or LAG525 + carboplatin). Duration of exposure will be categorized into time intervals; frequency counts and percentages will be presented for the number (%) of subjects in each interval. The number (%) of subjects who have dose reductions (for carboplatin), interruptions, and the reasons, will be summarized by treatment arm.

Subject level listings of all doses administered on treatment along with dose change reasons will be produced.

The safety set will be used for all summaries and listings of study treatment.

Duration of exposure to study treatment

Duration of exposure to study treatment is considered by taking into account the duration of exposure to LAG525, spartalizumab or carboplatin (as applicable depending on the treatment arm):

Duration of exposure to study treatment (weeks) = (last date of exposure to study treatment) – (date of first administration of study treatment) + 1.

The last date of exposure to study treatment is the latest of the last dates of exposure to LAG525, spartalizumab or carboplatin (as applicable depending on the treatment arm) (see [Table 2-5](#)).

Summary of duration of exposure of study treatment in appropriate time units will include categorical summaries (< 3 weeks, at least 3 weeks, at least 6 weeks, etc.) and continuous summaries (i.e. mean, standard deviation etc.) using appropriate units of time. Summary of cycles received will include categorical summaries (at least 1 cycle, at least 3 cycles, at least 5 cycles and etc).

Duration of exposure to LAG525, spartalizumab and carboplatin

Duration of exposure to LAG525 (weeks) = (last date of exposure to LAG525) – (date of first administration of LAG525) + 1.

Duration of exposure to spartalizumab (weeks) = (last date of exposure to spartalizumab) – (date of first administration of spartalizumab) + 1.

Duration of exposure to carboplatin (weeks) = (last date of exposure to carboplatin) – (date of first administration of carboplatin) + 1.

Table 2-3 Definition of last date of exposure of study drug

Study drug	Definition of last date of exposure of study drug	Example
------------	---	---------

LAG525 spartalizumab carboplatin	The planned end date of the last cycle in which the last non-zero dose of the investigational drug was last administered (i.e last date of administration + (planned interval duration-1day)) Note : If the subject died or was lost to follow-up before the derived last date, the last date of exposure to investigational drug is the date of death or the date of last contact, respectively. If the derived last date of exposure goes beyond the data cut-off date, it should be truncated to the date of data cut-off.	In a once every 3 weeks administration, the last date of exposure is the date of administration in the last cycle + 20 days
--	---	---

Summary of duration of exposure of LAG525, spartalizumab and carboplatin will include categorical summaries based on 21-day intervals (< 3 weeks, at least 3 weeks, at least 6 weeks, etc.) and using descriptive statistics (mean, standard deviation etc).

Cumulative dose

Cumulative dose of a study treatment is defined as the total dose given during the study treatment exposure and will be summarized for each of the study treatment components.

The **planned cumulative dose** for a study treatment component refers to the total planned dose as per the protocol up to the last date of investigational drug administration.

The **actual cumulative dose** refers to the total actual dose administered, over the duration for which the subject is on the study treatment as documented in the 'Study treatment – LAG525/PDR001/carboplatin' eCRF pages.

For subjects who did not take any drug component the cumulative dose for that component is by definition equal to zero.

For LAG525 and spartalizumab, the planned cumulative dose and actual cumulative dose will be expressed in mg.

For carboplatin, they will be expressed as calculated AUC (mg/mL x min). To that end the prescribed / administered dose in mg will be used to calculate the AUC using Calvert's formula based on the derived GFR value. Calvert's formula is given as:

- Carboplatin dosage (mg) = AUC (mg/mL x min) x [GFR (mL/min) + 25]

And the back-calculation for AUC is

- AUC (mg/mL x min) = Carboplatin dose (mg) / [GFR (mL/min) + 25]

For the calculation of GFR, creatinine value in the database with a measurement time closest to the dosing date and the subject's age and weight at the creatinine collection time will be used with the Cockcroft & Gault formula. If the interval between the measurement time and dosing time is the same before and after dose, the measurement corresponding to the time before dose will be used. Cockcroft & Gault's formula ([Cockcroft and Gault 1976](#)) is given as:

- Male GFR (mL/min) = $[140 - \text{age (years)}] \times \text{weight (kg)} \times 1.23 / \text{sCr } (\mu\text{mol/L})$
- Female GFR (mL/min) = $[140 - \text{age (years)}] \times \text{weight (kg)} \times 1.04 / \text{sCr } (\mu\text{mol/L})$

OR

- Male GFR (mL/min) = $[140 - \text{age (years)}] \times \text{weight (kg)} / [72 \times \text{sCr (mg/dL)}]$
- Female GFR (mL/min) = $[140 - \text{age (years)}] \times \text{weight (kg)} \times 0.85 / [72 \times \text{sCr (mg/dL)}]$

Note: The planned dose of carboplatin is per AUC 6 in general, but could be lower if the corresponding dose (mg) was higher than 900 mg (maximum dose in mg allowed as per the protocol). Hence if for a subject the first carboplatin dose prescribed was capped at 900 mg, the prescribed carboplatin dose (AUC) will be back calculated and will be used as planned dose in AUC to compute the planned cumulative dose.

Dose intensity and relative dose intensity

Dose intensity (DI) for subjects with non-zero duration of exposure is defined as follows:

For LAG525 and spartalizumab, $\text{DI (mg / cycle)} = \text{Actual Cumulative dose (mg)} / \text{Duration of exposure to study treatment (cycle)}$,

For carboplatin, $\text{DI (AUC / cycle)} = \text{Actual Cumulative dose (AUC)} / \text{Duration of exposure to study treatment (cycle)}$,

where $\text{Duration of exposure to study treatment (cycle)} = \text{Duration of exposure to study treatment (day)} / 21$. It will be rounded up to the nearest cycle if the last date of exposure to study treatment is replaced by the cut-off date: e.g. 66 days will be rounded to 4 cycles.

If for example, the duration of exposure to spartalizumab is 6 weeks and the subject receives two injections of spartalizumab 300 mg:

$$\begin{aligned} \text{DI (mg/cycle)} &= \text{Actual Cumulative dose (mg)} / \text{Duration of exposure (cycle)} \\ &= 600 \text{ (mg)} / (42/21) \text{ (cycle)} = 300 \text{ (mg/cycle)} \end{aligned}$$

For subjects who did not take any drug component the DI for that component is by definition equal to zero.

Planned dose intensity (PDI) is defined as follows:

For LAG525 and spartalizumab, $\text{PDI (mg / cycle)} = \text{Planned Cumulative dose (mg)} / \text{Duration of exposure (cycle)}$. PDI (mg / cycle) is 400 mg/cycle for LAG525 and 300 mg/cycle for spartalizumab.

For carboplatin, $\text{PDI (AUC / cycle)} = \text{Planned Cumulative dose (AUC)} / \text{Duration of exposure (cycle)}$.

Note: PDI (AUC / cycle) is AUC 6/cycle for carboplatin in general, but could be lower if the corresponding dose (mg) was higher than 900 mg. Hence if for a subject the first carboplatin dose prescribed is 900 mg, the prescribed carboplatin dose (AUC) will be back calculated and will be used as PDI per cycle for that subject.

Relative dose intensity (RDI) is defined as follows:

For LAG525 and spartalizumab, $RDI = DI \text{ (mg / cycle)} / PDI \text{ (mg / cycle)}$.

For carboplatin, $RDI = DI \text{ (AUC / cycle)} / PDI \text{ (AUC / cycle)}$.

DI and RDI will be summarized separately for each of the study treatment components, but using the duration of exposure of each of the components.

Some examples are given below on how to compute duration of exposure (cycle), planned/actual cumulative dose, PDI, DI and RDI in [Table 2-6](#) and [Table 2-7](#) for LAG525 and in [Table 2-8](#) and [Table 2-9](#) for carboplatin. For spartalizumab refer to LAG525 examples.

Table 2-4 Example 1 of LAG525 dose administration and exposure

Record number	Start/End Date	Dose Administered (mg)	Dose Stopped or Paused, Dose Interrupted?	Dose Permanently Discontinued	Reason
1	13Jun2018	400	No	No	
2	04Jul2018	400	No	No	
3	25Jul2018	400	No	No	
4	15Aug2018	0	Yes	No	AE

Duration of exposure (day) = (23Aug2018 = data cut-off date since LAG525 was not permanently discontinued) – (13Jun2018) + 1 = 72 days

Duration of exposure (cycle) for 72 days = 4 cycles (rounded from 3.4 cycles)

Planned cumulative dose (for 72 days, 4 cycles) = 1600 mg

Actual cumulative dose (for 72 days, 4 cycles) = 1200 mg

Dose intensity = (actual cumulative dose / duration of exposure in cycles) = 1200 mg / 4 cycles = 300 mg / cycle

Planned dose intensity = (planned cumulative dose / duration of exposure in cycle) = 1600 mg / 4 cycles = 400 mg / cycle

Relative dose intensity = $(DI / PDI) \times 100 = (300 \text{ mg/cycle}) / (400 \text{ mg/cycle}) \times 100 = 75\%$

Table 2-5 Example 2 of LAG525 dose administration and exposure

Record number	Start/End Date	Dose Administered (mg)	Dose Stopped or Paused, Dose Interrupted?	Dose Permanently Discontinued	Reason
1	13Jun2018	400	No	No	
2	04Jul2018	400	No	No	
3	25Jul2018	400	No	No	
4	15Aug2018	0	Yes	Yes	AE / AE

Duration of exposure (days) = (25Jul2018 + 20 days since LAG525 was permanently discontinued) – (13Jun2018) + 1 = 63 days

Duration of exposure (cycle) for 63 days = 3 cycles

Planned cumulative dose (for 63 days, 3 cycles) = 1200 mg

Actual cumulative dose (for 63 days, 3 cycles) = 1200 mg

Dose intensity = (actual cumulative dose / duration of exposure in cycle) = 1200 mg / 3 cycles
= 400 mg / cycle

Planned dose intensity = (planned cumulative dose / duration of exposure in cycle) = 1200 mg
/ 3 cycles = 400 mg / cycle

Relative dose intensity = (DI / PDI) x 100 = (400 mg/cycle) / (400 mg/cycle) x 100 = 100%

Table 2-6 Example 1 of carboplatin dose administration and exposure

Record number	Start/ End Date	Dose Prescribed (mg)	Dose Administered (mg)	Dose Prescribed (AUC)	Dose Administered (AUC)	Dose Permanently Discontinued
1	13Jun2018	800	800	6	6	No
2	04Jul2018	650	800	5	6	No
3	25Jul2018	650	650	5	5	No
4	15Aug2018	0	0	0	0	Yes

Duration of exposure (days) = (25Jul2018 + 20 days since carboplatin was permanently discontinued) – (13Jun2018) + 1 = 63 days

Duration of exposure (cycle) for 63 days = 3 cycles

Planned cumulative dose (for 63 days, 3 cycles) = 18 AUC

Actual cumulative dose (for 63 days, 3 cycles) = 17 AUC

Dose intensity = (actual cumulative dose / duration of exposure in cycle) = 17 AUC / 3 cycles
= 5.7 AUC / cycle

Planned dose intensity = (planned cumulative dose / duration of exposure in cycle) = 18 AUC
/ 3 cycles = 6 AUC / cycle

Relative dose intensity = (DI / PDI) x 100 = (17 AUC/cycle) / (18 AUC/cycle) x 100 = 94.4%

Table 2-7 Example 2 of carboplatin dose administration and exposure

Record number	Start/ End Date	Dose Prescribed (mg)	Dose Administered (mg)	Dose Prescribed (AUC)	Dose Administered (AUC)	Dose Permanently Discontinued
1	13Jun2018	900	900	5.9	5.9	No
2	04Jul2018	900	900	5.9	5.9	No
3	25Jul2018	750	750	5	5	No
4	15Aug2018	0	0	0	0	Yes

Duration of exposure (days) = (25Jul2018 + 20 days since carboplatin was permanently discontinued) – (13Jun2018) + 1 = 63 days

Duration of exposure (cycle) for 63 days = 3 cycles

Planned cumulative dose (for 63 days, 3 cycles) = $5.9 \times 3 \text{ AUC} = 17.7 \text{ AUC}$, as dose prescribed is 900 mg, the planned dose is the planned dose prescribed (AUC)

Actual cumulative dose (for 63 days, 3 cycles) = 15.8 AUC

Dose intensity = (actual cumulative dose / duration of exposure in cycle) = $15.8 \text{ AUC} / 3 \text{ cycles} = 5.3 \text{ AUC} / \text{cycle}$

Planned dose intensity = (planned cumulative dose / duration of exposure in cycle) = $17.7 \text{ AUC} / 3 \text{ cycles} = 5.9 \text{ AUC} / \text{cycle}$

Relative dose intensity = $(\text{DI} / \text{PDI}) \times 100 = (15.8 \text{ AUC/cycle}) / (17.7 \text{ AUC/cycle}) \times 100 = 89.3\%$

Dose reductions or interruptions

The number of subjects who have dose reductions, administration stopped/paused during infusion or interruptions, and the reasons, will be summarized separately for each of the study treatment components.

‘Dose changed’, ‘Dose interrupted’, “Was drug administration stopped or paused” fields from the ‘Study treatment’ eCRF pages for each study treatment component will be used to determine the dose reductions, dose interruptions and administration stopped /paused, respectively.

The corresponding fields ‘Reason for change’ and ‘Reason for administration stopped or paused’ will be used to summarize the reasons.

A dose change is either ‘change in prescribed dose level’ or ‘dosing error’ where actual dose administered is different from the prescribed dose.

For the purpose of summarizing interruptions and reasons, in case multiple entries for interruption are entered on consecutive dose administrations with different reasons, separate interruptions will be counted. However, if the reason is the same in this mentioned multiple entries on consecutive dose administrations, then it will be counted as one interruption.

Reduction: A dose change where the prescribed dose level is lower than the previous prescribed dose level. Any dose change to correct a dosing error will not be considered a dose reduction. Only dose change is collected in the eCRF, number of reductions will be derived programmatically based on the change and the direction of the change.

Note: No dose reductions are permitted for LAG525 or spartalizumab.

For carboplatin, it is considered as a reduction only if the difference between the previous prescribed dose in AUC and the current prescribed dose in AUC is greater than 15% of the previous prescribed dose in AUC.

Notes:

- A prescribed dose reduction lower than the previous prescribed dose, but where the administered dose is 0 mg or higher than the prescribed dose, will not be counted as a dose reduction: see records 10 and 11 in [Table 2-10](#).
- A decrease in dose from the protocol planned starting dose or a decrease from the previous non-zero dose will be counted as a dose reduction even if this decrease has been directly preceded by an interruption: see record 8 in [Table 2-10](#).

- If the dose decrease is followed by an interruption, with the dose resuming at the same level prior to the interruption, the second dose decrease or change in dosing frequency will not be counted as dose reduction: see record 6 in [Table 2-10](#).
- If, due to a dosing error, a subject receives higher than protocol planned starting dose and moves down to the planned starting dose then this is not a dose reduction: see record 3 in [Table 2-10](#). However if the change is directly from a higher than planned starting dose down to a lower than protocol planned starting dose, then this is a dose reduction.
- If, due to a dosing error, a subject receives lower than previous non-zero dose and resumes later at the protocol specified dose reduction, then lower dose received due to dosing error and protocol specified dose reduction are dose reductions.
- If, due to a dosing error, a subject receives lower than previous non-zero dose and resumes later at lower than previous non-zero dose, then 2 dose reductions will be counted.

Table 2-8 Examples of possible dose changes for carboplatin and dose reduction outcome

Record number	Prescribed dose (AUC)	Administered dose (AUC)	Counted as a dose reduction (Yes/No)	Comment
1	6	6	No	
2	6.5	6.5	No	Dose increased by error
3	6	6	No	Correcting dosing error
4	5	5	Yes	Prescribed dose reduction (e.g. due to AE)
5	0	0	No	Dose interruption
6	5	5	No	Resume previous dose
7	0	0	No	Dose interruption
8	5	4	No	Dosing error (not a prescribed dose reduction)
9	5	5	No	Correcting dosing error in row 8
10	4	0	No	Prescribed dose reduction (e.g. due to AE) but not administered due to dosing error
11	4	5	No	Prescribed dose reduction (e.g. due to AE) but not administered due to dosing error
12	4	4	Yes	Prescribed dose reduction (e.g. due to AE) and row 11 was not counted as a dose reduction (administered dose was 5 by error)

Treatment beyond RECIST progression

The number of subjects who continue treatment beyond RECIST1.1 progression according to local investigators assessment based on protocol specified criteria will be summarized. It includes all subjects who received any study treatment (i.e. at least one dose of LAG525, spartalizumab or carboplatin (including incomplete infusion)) after RECIST1.1 progression assessed by local investigators. Those subjects will be identified using the field “Will the subject continue treatment beyond disease progression as per RECIST1.1?” on the Verification for Treatment Beyond RECIST1.1 PD eCRF pages.

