6.1.5 Treatment duration

Study treatment will continue until the participant experiences one of the following: disease progression per investigator's assessment by RECIST 1.1 (if not meeting the criteria for treatment continuation beyond disease progression as stipulated in Section 6.1.5.1)

, unacceptable toxicity, pregnancy, treatment is discontinued at the discretion of the investigator or the participant, start of a new anti-neoplastic therapy, withdrawal of consent, lost to follow-up, death, or study is terminated by the sponsor.

The investigator may decide to stop carboplatin after 6 cycles, even if the above criteria are not met.

Participants who continue to derive clinical benefit from the treatment based on the investigator's evaluation may receive post-trial access (PTA). PTA means the provision of treatment to trial participants following their completion of this trial (EOT visit will be required prior to PTA). PTA will be provided until one of the following is met: participant no longer derives clinical benefit, investigator discontinues treatment, launch or reimbursement (where applicable), treatment fails to achieve registration in the trial participant's country, or the clinical program is discontinued for any other reason

Mechanisms for provision of PTA may include an extension phase to this study, a separate extension protocol, a rollover protocol, provision of the Novartis investigational product in a non-trial setting (known as post-study drug supply [PSDS]) when no further safety or efficacy data are required, or any other mechanism appropriate for the country.

The PTA mechanism must comply with local laws and regulations in the participating trial countries. If Novartis discontinues the PTA for this trial, Novartis will work with investigators to transition participants onto locally available alternative treatment, or standard of care.

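### The SAP's dose-intensity formula divides each drug's dose by whole-regimen exposure, against its own closing sentence and worked examples, and so understates dose intensity for any drug stopped before the others

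*SAP*

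**What the plan says.** SAP 2.4.1 defines two kinds of exposure time. The first belongs to the regimen: "The last date of exposure to study treatment is the latest of the last dates of exposure to LAG525, spartalizumab or carboplatin". The second belongs to each drug. For carboplatin it is "Duration of exposure to carboplatin (weeks) = (last date of exposure to carboplatin) – (date of first administration of carboplatin) + 1", with matching lines for LAG525 and spartalizumab.

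Under dose intensity and relative dose intensity, DI for every drug is its actual cumulative dose divided by "Duration of exposure to study treatment (cycle" (the unit bracket closes after the quoted words). The clause that follows converts that same regimen-level duration from days to cycles by dividing by 21.

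Further down, the subsection states: "DI and RDI will be summarized separately for each of the study treatment components, but using the duration of exposure of each of the components". The short spartalizumab illustration under the formula uses spartalizumab's own six weeks. The four worked examples (captioned Tables 2-4 to 2-7) each follow a single drug's dosing record.

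Planned dose intensity (PDI) is described in two ways: as planned cumulative dose over exposure duration, and as a fixed amount per cycle. The fixed amounts are 400 mg for LAG525, 300 mg for spartalizumab and, in the SAP's words, "PDI (AUC / cycle) is AUC 6/cycle for carboplatin in general", lower where the first dose was capped at 900 mg.

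Protocol 12.3 bases DI on actual exposure duration without settling which duration is meant once drugs stop at different times. On stopping, Protocol 6.1.5 says: "The investigator may decide to stop carboplatin after 6 cycles, even if the above criteria are not met". Protocol 6.5.1 also lets a participant who drops one or two drugs for toxicity stay on the remainder.

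**The concern.** The formula line and the closing sentence agree only when all components of an arm start and end together. Once carboplatin ends and the antibodies continue, or one drug is dropped for toxicity, they give different answers. A programmer who follows defined terms would code the regimen-level duration, because the formula and its conversion clause both name it.

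Dose intensity is among the endpoints listed for the safety objective (Protocol Table 2-1, SAP Table 1-1). With the regimen-level denominator, a carboplatin course that ended as the protocol permits would appear as reduced dosing. This would occur only in Arms 2 and 3, and it would grow with time spent on antibody afterwards. The table would then describe how long the other drugs ran rather than how carboplatin was delivered.

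**Working it through.** **Inputs**
- Cycle length: 21 days (Protocol 4.2; SAP conversion clause).
- Carboplatin PDI: AUC 6 per cycle (SAP 2.4.1), assuming no 900 mg cap.
- Six full carboplatin cycles: 6 × 6 = 36 AUC (stop after six cycles permitted by Protocol 6.1.5).
- Total regimen length T in cycles: assumed, 6 to 18. The plan states no expected value.

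**Reproducing the SAP's own examples**
- Carboplatin example 1 (Table 2-6): exposure ends 20 days after the last carboplatin dose, giving 63 days. 63/21 = 3 cycles; DI = 17/3 = 5.67 AUC per cycle (printed as 5.7); RDI = 17/18 = 94.4%, as printed.
- LAG525 example 1 (Table 2-4): 72 days, 72/21 = 3.4, rounded up to 4 cycles; DI = 1200/4 = 300 mg; RDI = 300/400 = 75%, as printed.
- LAG525 example 2 (Table 2-5): 63 days, 3 cycles; DI = 1200/3 = 400 mg; RDI = 100%, as printed.
- Carboplatin example 2 (Table 2-7) uses the same 63-day, single-drug duration. Its listed doses sum to 5.9 + 5.9 + 5 = 16.8 AUC, not the printed 15.8. That is a separate slip and does not bear on the denominator.

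Every example therefore rests on the drug's own exposure. None shows another component continuing after the drug stops.

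**Applying each rule to six full carboplatin cycles**

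Formula line, with PDI fixed at 6: DI = 36/T and RDI = (36/T)/6 = 6/T.
Component rule: DI = 36/6 = 6 AUC per cycle and RDI = 6/6 = 100% for every T.

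| T (cycles) | DI, formula line | RDI, formula line | DI, component rule | RDI, component rule |
|---|---|---|---|---|
| 6 | 6.0 | 100% | 6.0 | 100% |
| 7 | 5.1 | 86% | 6.0 | 100% |
| 8 | 4.5 | 75% | 6.0 | 100% |
| 10 | 3.6 | 60% | 6.0 | 100% |
| 12 | 3.0 | 50% | 6.0 | 100% |
| 18 | 2.0 | 33% | 6.0 | 100% |

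RDI reaches 50% only when 6/T ≤ 0.5, that is T ≥ 12 cycles, or 12 × 21 = 252 days.

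**Alternative reading of PDI**

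SAP 2.4.1 runs planned cumulative dose to the drug's last administration. If that is 36 AUC and PDI is also divided by T, then RDI = (36/T)/(36/T) = 100%. DI is still 36/T, for example 3.0 instead of 6.0 AUC per cycle at T = 12.

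**The case against.** The best defence is that the SAP already shows what it means. It opens 2.4.1 by promising separate summaries for each component, defines an exposure time for each drug, illustrates DI with spartalizumab's own exposure, works the examples from single-drug records, and closes with a sentence that reads as a deliberate qualification. Someone working from the examples would get 100% for six full carboplatin cycles. This stands as evidence of intent, and it identifies the correct fix. It does not remove the conflict, because the formula and its conversion clause still name the regimen-level term, and no example covers the case in which the two rules differ.

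A second defence is that RDI can cancel to 100%. That holds if PDI is taken over the same duration, but the SAP also fixes PDI per cycle, and DI, which is itself reported, is understated either way.

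A reader might infer that stopping carboplatin after six cycles generally yields an RDI of 50% or less. The documents do not support that. The value is 6/T, there is no distortion at T = 6, and 50% needs at least six further antibody cycles. The Amendment 4 summary does report three Arm 2 participants on treatment on 15-Feb-2021, 354 days (16.9 cycles) after the primary cut-off of 27-Feb-2020, so long regimens occurred. It does not say whether or when their carboplatin stopped.

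A reader might also infer a sevenfold error from the exposure formulas labelled in weeks, such as "Duration of exposure to study treatment (weeks) = (last date of exposure to study treatment", which give days. The SAP's division of days by 21, its 21-day bins and its equation of 6 weeks with 42 days make the intended unit clear. This is a label to correct, not a result that would be wrong.

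**Conclusion.** The denominator in the DI formulas is wrong as written and contradicts the rest of the same subsection. Taken literally, it understates DI for any drug that stops before another component of its arm. For six full carboplatin cycles the understatement is a factor of 6/T: none at 6 cycles, one quarter at 8, one half at 12. The same factor applies to RDI when PDI is held at AUC 6 per cycle, and vanishes from RDI if PDI uses the same duration.

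These figures assume full uncapped doses, no interruptions and a chosen T. Whether any reported table is affected depends on which line was programmed, which the documents do not show. The consequence is confined to descriptive exposure and safety summaries. The proof-of-preliminary-efficacy rule for response rate does not use dose intensity, and the SAP plans no inferential analysis for the close-out report.

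**What to change.** In SAP 2.4.1, in the DI formulas for all three drugs and in the clause converting days to cycles, replace the regimen-level duration with the duration of exposure to the component concerned. State that PDI uses that same component duration. Adding one worked example in which carboplatin stops while the antibodies continue would close the gap left by the existing ones.

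As an editorial correction, divide the four exposure formulas labelled in weeks by 7, or relabel them as days.

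The cost is a few words of SAP text and a check of the program that produces the dose-intensity tables. No new data are needed, and treatment and the primary analysis are untouched.

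### SAP 2.4.1 overstates dose intensity when death or loss to follow-up cuts the last cycle short, because only a cut-off truncation is rounded up to a whole cycle

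*SAP*

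**What the plan says.** SAP Table 2-3 credits each dose with its full planned interval. On a three-weekly schedule, "the last date of exposure is the date of administration in the last cycle + 20 days". It then shortens that date in three situations. For death or loss, "If the subject died or was lost to follow-up before the derived last date", then "the last date of exposure to investigational drug is the date of death or the date of last contact, respectively". For the data cut-off, "If the derived last date of exposure goes beyond the data cut-off date, it should be truncated to the date of data cut-off".

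Under Dose intensity and relative dose intensity, days are divided by 21 to give cycles, and the round-up applies to one of these situations only: "It will be rounded up to the nearest cycle if the last date of exposure to study treatment is replaced by the cut-off date", illustrated by "e.g. 66 days will be rounded to 4 cycles". Nothing is said about rounding for death or last contact. The worked examples cover a cut-off (rounded) and permanent discontinuation (exactly 63 days), so none settles the point. DI and RDI use each component's own duration.

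PDI is stated in two ways in the same section. One is a formula: planned cumulative dose over duration of exposure, with planned cumulative dose counted up to the last administration. The other is a constant: "PDI (mg / cycle) is 400 mg/cycle for LAG525 and 300 mg/cycle for spartalizumab".

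Protocol section 12.3 gives only the general ratio of cumulative dose to actual duration of exposure.

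**The concern.** The full cycle dose is given on Day 1, so DI is comparable between participants only if each dose is matched with a full cycle of time. The SAP does this for participants who stop treatment (dose date + 20 days) and for those cut by the cut-off (rounding up). It does not do so for those who die or are lost within the last cycle. Two participants with the same doses and the same number of days on study then get different DI, depending only on why the cycle ended.

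Dose intensity is a listed endpoint of the secondary safety objective (protocol Table 2-1, SAP Table 1-1). Compared with crediting the last cycle in full, the error always raises DI, and it is largest in participants with the fewest doses.

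**Working it through.** **Inputs.** Cycle of 21 days; LAG525 400 mg, spartalizumab 300 mg, carboplatin AUC 6 per cycle (protocol Table 6-2); truncation from SAP Table 2-3; rounding and PDI from SAP 2.4.1.

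**Formulas.** Days = last date of exposure − first dose + 1. Cycles = days / 21, rounded up only for a cut-off. DI = actual cumulative dose / cycles. RDI = DI / PDI.

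**The plan's own figures.**
- 66/21 = 3.14, rounded to 4 cycles, as stated.
- LAG525 Example 1 (cut-off): 72/21 = 3.43, rounded to 4; DI = 1200/4 = 300; RDI = 300/400 = 75%, as stated.
- LAG525 Example 2 (discontinued): 63/21 = 3; DI = 1200/3 = 400; RDI = 100%, as stated.

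**Death or last contact, all doses on time.** With n doses and the end k days after the last one, days = 21(n − 1) + k + 1. For LAG525 and k = 7:

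| Doses | Days | Cycles, unrounded | DI as written | DI if cut-off fell that day |
|---|---|---|---|---|
| 1 | 8 | 0.381 | 400/0.381 = 1050 | 400/1 = 400 |
| 3 | 50 | 2.381 | 1200/2.381 = 504 | 1200/3 = 400 |
| 6 | 113 | 5.381 | 2400/5.381 = 446 | 2400/6 = 400 |

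The multipliers (2.625, 1.26, 1.115) do not depend on the dose, so spartalizumab and carboplatin are inflated in the same proportion.

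**Range over k.** After a single dose, DI is 8400 at k = 0, 1200 at k = 6, 600 at k = 13 and 420 at k = 19. At k = 20 the cycle is complete and DI = 400. The excess therefore exists only for k = 0 to 19.

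**RDI under each PDI statement (k = 7).**
- Fixed PDI of 400: 1050/400 = 262.5%; 504/400 = 126%; 446/400 = 111.5%.
- Formula PDI: planned and actual cumulative dose are equal and share the same duration, so PDI is also 1050, 504 or 446, and RDI = 100%.

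For whole cycles and on-time dosing the two statements agree. Here they do not.

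**Off-schedule dosing.**
- Doses on days 1 and 25, death on day 43. As written: 800/(43/21) = 391. Last cycle credited in full (to day 45): 800/(45/21) = 373. Rounded up: 800/3 = 267.
- Doses on days 1 and 43, the day 22 dose omitted, death on day 49. As written: 800/(49/21) = 343. Last cycle credited in full (to day 63): 800/3 = 267.

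**The case against.** Four points can be made for the plan.

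**Convention.** Protocol 12.3 refers to actual duration of exposure, and ending exposure at death fits those words. This does not rescue the rule. The SAP already departs from elapsed time by adding 20 days after the last dose and by rounding cut-off cases; having chosen to credit whole intervals, it leaves out one group.

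**RDI.** The LAG525 and carboplatin worked examples compute PDI by the formula, under which duration cancels and RDI is 100% for on-time dosing. This stands. A reader might infer that RDI is inflated for everyone who dies mid-cycle. The documents support that only on the fixed-PDI reading.

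**Size.** A reader might infer a material distortion between arms. With fixed PDI and everyone else at 100%, one single-dose death on day 8 would move mean RDI in an arm of 34 by (262.5 − 100)/34 = 4.8 points. That is an extreme case: the 3-dose and 6-dose cases above move it by 26/34 = 0.8 and 11.5/34 = 0.3 points. The documents give no count of deaths or losses within 20 days of a dose, so no arm difference can be claimed. Protocol 12.3 also asks for medians, quartiles and extremes, and the SAP tabulates interruptions directly from the eCRF, so an outlier would be visible and interruptions would not be hidden.

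**Remedy.** Extending the round-up to death and last contact is the obvious repair, but it overcorrects after a delay. In the day 1 and day 25 example it gives 267, against 373 with the last cycle credited in full; the current text, at 391, is closer. This objection stands and determines the form of the fix.

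**Conclusion.** The rule as written gives a DI that is too high whenever death or last contact falls 0 to 19 days after the last dose of a component. Too high means relative to crediting the last cycle in full, as is done for other participants. For on-time LAG525 with death 7 days after the last dose, the values are 1050, 504 and 446 mg/cycle after 1, 3 and 6 doses, against 400.

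It would go too far to say that DI always exceeds the per-cycle dose given. That is certain only with on-time dosing: with one omitted dose, DI was 343, below 400, although still above the 267 it should be.

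RDI above 100% (262.5%, 126%, 111.5%) rests on PDI being the fixed value. Under the formula it is 100%. The firm finding on RDI is that the SAP's two PDI statements disagree for these participants, so two programmers could report different results.

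Only descriptive exposure summaries are affected. The response-rate analysis and the proof-of-preliminary-efficacy decision do not use these quantities. The number of participants affected is unknown. The point is worth correcting because a stated rule gives a wrong value for a listed safety endpoint and the change is small.

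**What to change.** In SAP 2.4.1, define a separate duration for the DI and RDI denominator of each component: first administration to last administration + 20 days, without truncation at death or last contact. Keep the truncation in Table 2-3 for the duration-of-exposure summary, and leave the cut-off rule as it is. State that PDI uses this same duration.

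On-time dosing then gives n cycles for n doses, DI = 400 mg/cycle, formula PDI = 400 and RDI = 100%, whatever ended the last cycle. The delayed-dose example gives 373 and the omitted-dose example 267. The formula and the fixed PDI agree for on-schedule dosing. Off schedule they can still differ, so the SAP should also say which one governs.

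The cost is a sentence or two in the SAP and one extra derived duration variable. The downside is that, for these participants, the DI denominator will differ from the reported exposure duration, which needs a table footnote.
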